## 11.2 Clinical Laboratory Assessments

Descriptive statistics for clinical laboratory values (in SI units) at baseline, postbaseline, and changes from baseline values at each postbaseline timepoint will be presented by treatment group for the following laboratory parameters:

Hematology:	Absolute and differential white blood cell count, erythrocyte count, hemoglobin, hematocrit, platelet count, and red blood cell indices (mean corpuscular volume, mean corpuscular hemoglobin, and mean corpuscular hemoglobin concentration)
Chemistry:	Sodium, potassium, calcium, chloride, bicarbonate, magnesium, gamma glutamyl transferase, phosphate, glucose, blood urea nitrogen, creatinine, creatine phosphokinase, total protein, alkaline phosphatase, albumin, bilirubin (total; direct; indirect), ALT, AST, total cholesterol, low-density lipoprotein, high-density lipoprotein, triglycerides
Urinalysis:	Specific gravity, pH, protein, glucose, ketones, and blood

In addition, descriptive statistics for values and changes from the baseline values in conventional units at each assessment time point will be presented for selected clinical laboratory parameters listed in [Table 11-1](#).

**Table 11-1** List of Selected Parameters Reported in Conventional Unit

Number	Laboratory Parameter	Conventional Unit
1	Alanine Aminotransferase (SGPT)	U/L
2	Albumin	G/dL
3	Alkaline Phosphatase	U/L
4	Aspartate Aminotransferase (SGOT)	U/L
5	Bilirubin, Direct (Conjugated)	mg/dL
6	Bilirubin, Indirect (Unconjugated)	mg/dL
7	Bilirubin, Total	mg/dL
8	Blood Urea Nitrogen	mg/dL
9	Calcium	mg/dL
10	Cholesterol, HDL	mg/dL
11	Cholesterol, LDL	mg/dL
12	Cholesterol, LDL direct and calculated (combined) (This lab parameter could be the same as #11)	mg/dL
13	Cholesterol, Total	mg/dL
14	Creatine Kinase	U/L
15	Creatinine	mg/dL
16	Glucose	mg/dL
17	Insulin	uIU/mL
18	Triglycerides	mg/dL

Number	Laboratory Parameter	Conventional Unit
19	Uric Acid	mg/dL
20	Hemoglobin	G/dL

Clinical laboratory test values will be considered potentially clinically significant (PCS) if they meet either the lower-limit or higher-limit PCS criteria listed in Table 11-2. The number and percentage of participants who have PCS postbaseline clinical laboratory values will be tabulated by treatment group for the double-blind treatment period. The percentages will be calculated relative to the number of participants with available non-PCS baseline values and at least 1 postbaseline assessment for the double-blind treatment period. The numerator will be the total number of participants with available non-PCS baseline values and at least 1 PCS postbaseline value for the double-blind treatment period. A supportive tabular display of participants with PCS postbaseline values will be provided, including the PID number, baseline and all postbaseline (including non-PCS) values.

In addition, a tabular display showing all AEs that occurred in participants who had PCS postbaseline clinical laboratory values will be provided.

The number and percentage of participants meeting potential Hy's Law criteria (elevation of alanine aminotransferase [ALT] or aspartate aminotransferase [AST]  $\geq 3x$  ULN with total bilirubin  $\geq 2x$  ULN and alkaline phosphatase  $< 2x$  ULN in a 24-hour period) will be tabulated by double-blind treatment group starting from the first dose of double-blind study treatment to within 30 days after the last dose of double-blind study treatment for the Safety Population. A supportive listing will also be provided.

**Table 11-2 Criteria for Potentially Clinically Significant Laboratory Values**

Laboratory Parameter	SI Unit	Conversion Factora	Conventional Unit	PCS Criterionb Low Value	PCS Criterionb High Value
Hematology					
Hemoglobin	g/L	0.1	g/dL	$< 0.9 \times \text{LLN}$	—
Hematocrit	Volume fraction	100	%	$< 0.9 \times \text{LLN}$	—
Eosinophils	%	1	%	—	$> 10$
Neutrophils	%	1	%	$< 30$	$> 90$
Basophils	%	1	%	—	$> 6$
Monocytes	%	1	%	—	$> 20$
Lymphocytes	%	1	%	$< 10$	$> 60$
Absolute neutrophil count	$\times 10^9/\text{L}$	1	1000/ $\mu\text{L}$	$< 1.0$	—
Platelet count	$\times 10^9/\text{L}$	1	1000/ $\mu\text{L}$	$\leq 75$	$\geq 700$
White blood cell count	$\times 10^9/\text{L}$	1	1000/ $\mu\text{L}$	$\leq 2.5$	$\geq 15$
Chemistry					
Albumin	g/L	0.1	g/dL	$< 0.9 \times \text{LLN}$	$> 1.1 \times \text{ULN}$
Alkaline phosphatase	U/L	1	U/L	—	$\geq 3 \times \text{ULN}$
Alanine aminotransferase	U/L	1	U/L	—	$\geq 3 \times \text{ULN}$

**Table 11-2 Criteria for Potentially Clinically Significant Laboratory Values**

Laboratory Parameter	SI Unit	Conversion Factora	Conventional Unit	PCS Criterionb Low Value	PCS Criterionb High Value
(ALT)					
Aspartate aminotransferase (AST)	U/L	1	U/L	—	$\geq 3 \times \text{ULN}$
Gamma-glutamyl transferase (GGT)	U/L	1	U/L	—	$\geq 3 \times \text{ULN}$
Lactate dehydrogenase (LDH)	U/L	1	U/L	—	$\geq 3 \times \text{ULN}$
Blood urea nitrogen or Urea	mmol/L	2.8011	mg/dL	—	$> 1.2 \times \text{ULN}$
Calcium	mmol/L	4.008	mg/dL	$< 0.9 \times \text{LLN}$	$> 1.1 \times \text{ULN}$
Chloride	mmol/L	1	mg/dL	$< 0.9 \times \text{LLN}$	$> 1.1 \times \text{ULN}$
Total cholesterol	mmol/L	38.6698	mg/dL	—	$> 1.3 \times \text{ULN}$
High-density lipoprotein (HDL) cholesterol	mmol/L	39	mg/dL	$< 0.8 \times \text{LLN}$	—
Low-density lipoprotein (LDL) cholesterol	mmol/L	39	mg/dL	—	$> 1.2 \times \text{ULN}$
Creatine phosphokinase (CPK)	U/L	1	U/L	—	$> 1.5 \times \text{ULN}$
Creatinine	$\mu\text{mol/L}$	0.0113	mg/dL	—	$> 1.3 \times \text{ULN}$
Glucose, fasting	mmol/L	18.018	mg/dL	$< 0.8 \times \text{LLN}$	$> 1.2 \times \text{ULN}$
Magnesium	mmol/L	2	mEq/L	$< 0.9 \times \text{LLN}$	$> 1.1 \times \text{ULN}$
Potassium	mmol/L	1	mEq/L	$< 0.9 \times \text{LLN}$	$> 1.1 \times \text{ULN}$
Sodium	mmol/L	1	mEq/L	$< 0.9 \times \text{LLN}$	$> 1.1 \times \text{ULN}$
Total bilirubin	$\mu\text{mol/L}$	0.0585	mg/dL	—	$> 1.5 \times \text{ULN}$
Total protein	g/L	0.1	g/dL	$< 0.9 \times \text{LLN}$	$> 1.1 \times \text{ULN}$
Triglycerides, fasting	mmol/L	88.4956	mg/dL	—	$> 1.2 \times \text{ULN}$
Uric acid or Urate	$\mu\text{mol/L}$	0.0168	mg/dL	—	$> 1.1 \times \text{ULN}$
Urinalysis					
Protein	—	—	—	—	At least 2 +
Glucose	—	—	—	—	At least 2 +
Blood	—	—	—	—	At least 2 +

a Conversion factor from SI units to conventional (traditional) units.

b Criteria refer to SI units.

Blood urea nitrogen or Urea are the same parameters, and Uric acid or Urate are the same parameters.

LLN = lower limit of normal; PCS = potentially clinically significant; SI = *Le Système International d'Unités* (International System of Units); ULN = upper limit of normal laboratory reference range.

### 11.3 Vital Signs

Descriptive statistics for vital signs (systolic and diastolic blood pressures, pulse rate, and weight) values at baseline, postbaseline, and changes from baseline values at each postbaseline timepoint will be presented by treatment group.

Vital sign values will be considered PCS if they meet both the observed value criterion and the change from baseline value criterion, if both criteria are available, or meet either the observed

value criterion or the change from baseline value criterion that will be detailed in [Table 11-3](#). The number and percentage of participants who have PCS postbaseline vital sign values will be tabulated by study treatment for each assessment. The percentages will be calculated relative to the number of participants who have available baseline or non-PCS baseline (for parameters with only the observed value criterion) values and at least 1 postbaseline assessment. The numerator will be the total number of participants with at least 1 PCS postbaseline value. A supportive listing of participants with PCS postbaseline values will be provided. In addition, a tabular display showing all AEs that occurred in participants who had PCS postbaseline vital sign values will be provided.

**Table 11-3** Criteria for Potentially Clinically Significant Vital Signs

Parameter	Flag	Criteriaa	
		Observed Value	Change From Baseline
Supine systolic blood pressure, mm Hg	High	$\geq 180$	Increase of $\geq 20$
	Low	$\leq 90$	Decrease of $\geq 20$
Supine diastolic blood pressure, mm Hg	High	$\geq 105$	Increase of $\geq 15$
	Low	$\leq 50$	Decrease of $\geq 15$
Supine pulse rate, bpm	High	$\geq 120$	Increase of $\geq 15$
	Low	$\leq 50$	Decrease of $\geq 15$
Weight, kg	High	—	Increase of $\geq 7\%$
	Low	—	Decrease of $\geq 7\%$

a A postbaseline value is considered potentially clinically significant if it meets both the observed-value and the change-from-baseline criteria.

bpm = beats per minute.

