AE = adverse event; BPRS+ = Brief Psychiatric Rating Scale - Positive Symptoms Subscale; CADSS = Clinician Administered Dissociative States Scale; CGI-S = Clinical Global Impressions-Severity; C-SSRS = Columbia–Suicide Severity Rating Scale; C-VISA = Clinical Validation Inventory for Study Admission; DSM = *Diagnostic and Statistical Manual of Mental Disorders*; DxV = Diagnostic Validation; ECG = electrocardiogram; ET = Early Termination; MADRS = Montgomery-Åsberg Depression Rating Scale; PK = pharmacokinetic; SCID = Structured Clinical Interview for DSM disorders; SDC = Symbol Digit Coding

a Performed for all participants, including those prematurely discontinued after randomization. Clinically significant findings upon termination should be followed until the condition returns to prestudy status or can be explained as unrelated to study treatment. If necessary, additional follow-up visits can be scheduled.

b Participants will be requested to fast overnight or for at least 8 hours before arriving at the study center for appointments involving the collection of clinical

laboratory blood tests. Clinical laboratory tests can be done at any visit for safety reasons at the discretion of the investigator.

- c Height will only be measured at Visit 1 (Screening); pulse rate, blood pressure, temperature, and body weight will be assessed at every visit. Blood pressure and pulse will be assessed while the participant is supine and standing.
- d PK sampling is optional. For participants who consent to participate, samples will be collected at Visit 2/2a (Day 1) at 1 hour ( $\pm$  15 minutes), 2 hours ( $\pm$  15 minutes), and 4 hours ( $\pm$  15 minutes) post dose. At Visit 5 (Day 8), a single sample will be collected any time from 15 minutes to 3 hours post dose; site staff should record the time of the prior meal taken by the participant before the PK sample collection, whenever possible.

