Like rapastinel, AGN-241751 is a novel NMDAR modulator with partial agonist properties. AGN-241751 has appropriate oral bioavailability and blood brain barrier penetration.

In support of AGN-241751 investigation in human subjects, a series of nonclinical pharmacology studies have been performed. These studies were designed to characterize AGN-241751 in terms of its potential to a) potentiate NMDAR activity; b) strengthen NMDAR-dependent LTP; and c) produce antidepressant-like effects in rat models. Additional safety and tolerability studies were carried out to evaluate AGN-241751's side effect profile, including potential ataxic/sedative and pro-convulsive effects. Besides displaying potent partial agonist activity at NMDAR, AGN-241751 increased NMDAR-dependent synaptic plasticity in rat hippocampus and medial prefrontal cortex in vitro and ex vivo. AGN-241751 was active in several models of depression, and has demonstrated rapid onset of action in rat models of depression without causing CNS side effects. AGN-241751 had no appreciable affinity for over 60 neurotransmitter-receptors and ion channels in a CEREP screen indicating a lack of potential off-target effects. Central nervous system safety and tolerability profile of AGN-241751 was favorable at substantially higher doses relative to its antidepressant doses. Although transient lowering of blood pressure in conscious telemetered dogs was observed in cardiovascular safety studies, there were no findings that preclude its use for further development. In other safety pharmacology studies, AGN-241751 was not associated with any adverse effects. In summary, the safety profile of AGN-241751 supports the proposed clinical doses in Phase 2a (0.25 mg to 10 mg).

Following oral administration, mean oral bioavailability of AGN-241751 in rats and dogs was approximately 100% and 99%, respectively. There was no accumulation after repeat administration and AGN-241751 was rapidly distributed to the target tissue (brain) with time to

reach maximum concentration ( $T_{max}$ ) at 1 hour post dose in rats. Brain to plasma and cerebrospinal fluid (CSF) to plasma area under the concentration-time curve (AUC) ratios were 0.16 and 0.3, respectively.

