#### **9.4.2. Vital Signs**

Vital signs (pulse rate, systolic and diastolic blood pressure, oral or tympanic temperature, and body weight) will be assessed at every visit. Height will be assessed at Visit 1 (Screening).

Blood pressure and radial pulse rate will be measured in the supine position followed by the standing position. The standing measurements should be assessed after a sufficient amount of time (approximately 1-3 minutes) has been elapsed to allow the BP to equilibrate in the standing state.

Radial pulse rate should be measured after blood pressure measurements. Blood pressure may be measured manually or by machine, but radial pulse rate should only be measured manually and for a sufficient time to acquire an accurate measurement.

Participants should be instructed not to wear clothing with tight sleeves when they come for clinic visits. Additionally, participants should be kept as calm and undisturbed as possible while blood pressure and pulse rate measurements are taken (eg, there should be no talking while the blood pressure is being measured). The same arm and blood pressure cuff (appropriate to the arm circumference) should be used for all blood pressure measurements.

Whenever possible, the participant's weight will be measured at the same time of day; participants should wear their usual indoor clothing, but take off their jacket and shoes. For each participant, body weight should be determined using the same equipment during the study after ensuring its proper calibration.

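### SAP Table 11-3 flags blood pressure and pulse on supine values only, so a fall on standing with normal supine values is not counted in the PCS outputs

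*SAP*

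**What the plan says.** **Collection.** Footnote c of the schedule of activities (Protocol Section 2) states that "pulse rate, blood pressure, temperature, and body weight will be assessed at every visit" and that "Blood pressure and pulse will be assessed while the participant is supine and standing"; the SAP repeats the footnote under its Table 5-1. The vital signs row is marked at every visit, including Visit 2a, 4 hours after the first dose. Protocol 9.4.2 sets the order: "Blood pressure and radial pulse rate will be measured in the supine position followed by the standing position". The standing reading follows after about 1 to 3 minutes, to let the pressure settle.

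**Flagging.** Protocol 10.4.2.3 leaves the PCS criteria to the SAP. The blood pressure and pulse rows of SAP Table 11-3 are "Supine systolic blood pressure, mm Hg", "Supine diastolic blood pressure, mm Hg" and "Supine pulse rate, bpm". Each requires an extreme observed value together with a change from baseline. The only other row is weight, on change alone.

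**Descriptive statistics.** SAP 11.3 and Protocol 10.4.2.3 plan summaries of blood pressure and pulse at each timepoint by treatment, without naming the position.

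**Background.** Protocol Section 3 reports that "transient lowering of blood pressure in conscious telemetered dogs was observed in cardiovascular safety studies", and adds that nothing found stood in the way of further development.

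**The concern.** The supine-then-standing sequence with a timed wait is a postural measurement, yet no planned PCS rule uses the standing half of it. The PCS criteria are the only uniform, by-dose count of individual vital sign abnormalities in the plan. A participant whose pressure falls on standing while the supine readings stay normal is missed by that count. The participant is also missed by the two outputs keyed to it: the supportive listing, and the display of AEs in participants with PCS vital signs.

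At stake is a descriptive safety comparison across four doses and placebo. Protocol 10.1.3 says the study is meant to inform Phase 3 doses, and blood pressure lowering is the cardiovascular finding that the Introduction reports, so a by-dose view of postural change is relevant. No efficacy result or error rate is touched.

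**Working it through.** The plan gives no figure of its own to reproduce. The check is one of coverage, followed by the rule applied to example readings.

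**1. What is collected against what is flagged**

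| Measurement | Collected | Criterion in SAP Table 11-3 |
|---|---|---|
| Supine systolic, mm Hg | every visit | low: ≤90 and fall ≥20; high: ≥180 and rise ≥20 |
| Supine diastolic, mm Hg | every visit | low: ≤50 and fall ≥15; high: ≥105 and rise ≥15 |
| Supine pulse, bpm | every visit | low: ≤50 and fall ≥15; high: ≥120 and rise ≥15 |
| Standing systolic, diastolic, pulse | every visit | none |
| Standing minus supine, same visit | derivable | none |

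Falls and rises in the table are changes from baseline. No orthostatic criterion appears elsewhere in the SAP or in Protocol 10.4.2.3.

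**2. A fall on standing with a normal supine value**

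Take supine systolic 120 and standing 92 (illustrative). The fall is 120 − 92 = 28 mm Hg. The supine value is above 90 and below 180, so neither the low nor the high row can be met, whatever the baseline was. There is no flag.

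**3. A larger fall (assumed readings)**

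Baseline supine 120/78, pulse 70. Post-dose supine 118/76, pulse 72. Post-dose standing 84/50, pulse 104.

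- Postural change: 118 − 84 = 34 systolic; 76 − 50 = 26 diastolic; 104 − 72 = +32 bpm.
- Table 11-3 on supine values: systolic 118 > 90 with a fall of 2; diastolic 76 > 50 with a fall of 2; pulse 72 < 120 with a rise of 2. There is no flag.

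**4. Would copying the existing limits to standing rows be enough?**

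Assume a standing baseline of 118/80.

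- Standing 84/50: 84 ≤ 90 with a fall of 118 − 84 = 34, and 50 ≤ 50 with a fall of 80 − 50 = 30. Both are flagged.
- Standing 95/62, with supine still 118/76: the postural fall is 118 − 95 = 23 and 76 − 62 = 14. But 95 > 90 and 62 > 50, so there is no flag.
- Standing 92 from step 2: 92 > 90, so again no flag.

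Standing rows with the same limits would catch only the more extreme cases. A within-visit difference is needed to identify the rest.

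**5. How many participants might this concern?**

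The documents give no rate, so the rates below are assumptions. With n = 50 per group (SAP Section 14), the expected number is n × p and the chance of at least one is 1 − (1 − p)^50, where p is the proportion with such a fall and no supine flag.

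| Assumed p | Expected in 50 | Chance of at least one |
|---|---|---|
| 2% | 1 | 0.64 |
| 5% | 2.5 | 0.92 |
| 10% | 5 | 0.995 |
| 20% | 10 | about 1.00 |

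At each rate, the planned blood pressure and pulse PCS rows would count none of these participants. That follows from the definition of p and is not an estimate of harm.

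**The case against.** **Other routes exist.** A reader might infer that an orthostatic fall cannot be seen at all, or that the safety conclusions ignore the standing data. The documents do not support that.

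- Protocol Appendix 4 makes a vital sign abnormality an AE when the investigator judges it clinically significant, and AEs are tabulated by treatment group.
- SAP 16.2 puts all assessments in the data listings.
- The descriptive statistics are not restricted to supine readings, and the table specifications sit in a separate document (SAP Section 4) that may already include standing values.

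All of this stands, and it limits the point to the PCS outputs. It does not close the gap: AE reporting depends on individual judgment, group means can hide individual falls, and a listing is not a prespecified by-dose count.

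**The dog finding.** A reader might also take it as evidence of an orthostatic effect. It is described as transient lowering, with no mention of posture, and was judged not to preclude development. The supine low rows already address a general fall. The protocol also reports acceptable tolerability in healthy volunteers at 50 mg once and 25 mg daily for 10 days, against a top dose here of 10 mg weekly. The finding makes the gap relevant and shows no more than that.

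**The 4-hour reading.** The protocol describes rapid absorption and clearance and a short half-life, but gives no half-life figure. Whether appreciable drug remains at 4 hours is not established. The 4-hour timepoint is already a separate derived visit in SAP Table 16-1.

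**Cut-offs.** The sizes in Table 11-3 are changes from baseline paired with an observed-value limit. Reusing them as within-visit differences is a different contrast. Without a baseline condition they would also flag participants who had a postural fall before dosing, which is plausible because stable antihypertensives are permitted (Protocol Appendix 6). This stands and shapes the fix.

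**Conclusion.** The gap is real and limited. Followed as written, SAP 11.3 leaves every standing blood pressure and pulse reading out of the PCS tabulation, its supportive listing and the AE display keyed to it. A participant whose supine values meet no criterion is not counted on blood pressure or pulse, however large the fall on standing.

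This rests on the text of Table 11-3 and needs no assumption about event rates. How many participants it would affect is unknown: the 2% to 20% range above is assumed. The documents do not show that the drug has a postural effect, nor that such an effect would go wholly unnoticed. The consequence is an incomplete by-dose safety count in a Phase 2a study, which should be corrected because the data are already being collected.

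**What to change.** In SAP 11.3:

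1. State that descriptive statistics are given for supine, standing and standing-minus-supine systolic pressure, diastolic pressure and pulse.
2. Add a prespecified standing-minus-supine flag to Table 11-3, tabulated by treatment group at each derived visit; 4 hours post dose is already one.
3. Count only participants who do not meet the flag at the pre-dose baseline. This matches the non-PCS-baseline denominator that SAP 11.3 uses for parameters with an observed-value criterion alone. Write the condition into the numerator as well, because the vital signs numerator sentence does not repeat it.
4. Have the sponsor set and justify the cut-offs before unblinding. The table's existing change sizes (systolic 20 mm Hg, diastolic 15 mm Hg, pulse 15 bpm) may serve as a starting point. These are analysis flags, not rules for managing participants.

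The cost is a few table rows and one summary, with no new data. Some flags will reflect normal variability; the placebo group gives the comparison for reading them. SAP Section 4 cites Protocol Amendment 1 as the most recent, while the protocol is at Amendment 2, so a revision that aligns the two could carry this change.

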## 11.4 Electrocardiograms

Descriptive statistics for ECG parameters (ie, heart rate, PR interval, QRS interval, QT interval, and QTc interval) at baseline, postbaseline, and changes from baseline values at each postbaseline timepoint will be presented by treatment group.

ECG parameter values are considered PCS if ECG values meeting *either* the actual value or change from baseline PCS high criteria listed in [Table 11-4](#). The number and percentage of participants with PCS postbaseline values will be tabulated by study treatment. The percentages

will be calculated relative to the number of participants with an available non-PCS baseline value and at least one postbaseline assessment. The numerator will be the total number of participants with an available non-PCS baseline value and at least one PCS postbaseline ECG value. A supportive listing of participants with PCS postbaseline values will be provided and will include the participant number and the baseline and postbaseline values.

